12. DATA AND SPECIMEN BANKING*

NA

13. Data Analysis and Management*

Feasibility: We have conducted a preliminary analysis of billing data from 2019 from the ED at the University Campus, and this analysis suggests that we will be able to target a large population of potential participants. In one year, there were 2,275 adult visits with a primary or secondary diagnosis of diabetes, hyper-, or hypoglycemia (Table 1). Over 60% of these patients were discharged home from the ED, and the majority had type 2 diabetes, although type 1 diabetes was over-represented (15%) compared to its frequency among cases of diabetes in the general population (less than 10%). Emergency physicians tend not to bill for diagnoses that do not require active ED management, so our numbers are likely not an overestimate. We suspect that only a fraction of these patients will be eligible for our study, but even if we were to recruit one out of every four, we would exceed our recruitment goal (200) within a year.

Sample Size: The primary outcomes are the clinic attendance rate and the change in diabetes-related distress, as measured by the Diabetes Distress Scale (DDS) and PAID-5 scale between the ED visit and the follow-up appointment date (19). Secondary outcomes include repeat ED/EMS utilization over 6 months, repeat hospitalizations, major cardiovascular events, and changes in hemoglobin A1c. For clinic attendance, we will aim to achieve attendance at 80% of the scheduled clinic visits. For a one-sided test at alpha=0.025 of a single proportion against a standard proportion (0.80), we will have 80% power to detect a difference of 0.13 (0.80 – 0.67) with a sample size of 83 subjects in the CGM group. Adjusted for 20% dropout, we will need approximately 100 subjects/group. For the DDS outcome, we will compare the change from baseline to the end of follow-up in the DDS between the two groups. Although we will fit the trajectory of the DDS change in each group using all DDS measures in a mixed effects model with repeated measures (MMRM), for simplicity in sample size estimation, we will calculate the sample size for an unadjusted comparison of the change between the two treatment groups. Based on a study of 267 subjects with diabetes (19), the standard deviation of the DDS was 1.0 across the three sites in that study. The DDS is a questionnaire of 17 questions, each scored on a Likert scale of 1 (not a serious problem) to 6 (serious problem), with the overall score calculated as the mean score across the 17 items. Thus, the range of the overall score is 1.0 – 6.0. With 100 subjects in each group, we can detect a difference of about 0.40 in the DDS change between the two groups. The literature on the DDS does not identify a clinically meaningful difference although Fisher, Polonsky, Hessler, Mullan (2012) suggest a difference of 0.5 as meaningful (20). Thus, our sample size will achieve power of greater than 80% to detect that difference.

Analysis Strategy: As indicated in the Sample Size section above, for the clinic attendance rate, we will conduct the initial unadjusted analyses using an exact test of the frequencies under the presumed population proportion (0.80) and the observed proportion. Adjusted analyses will be conducted using a logistic regression model for the proportion of clinic visits attended as the outcome in the intervention group with predictors including age, gender, time since diagnosis of diabetes, and other factors of interest.

For the outcome of change in DDS, we will conduct the initial unadjusted analysis as described above in the Sample Size section. For adjusted analyses, we will include each DDS score in the longitudinal MMRM, so that we can model the trajectory of change as well as the individual changes over the period of follow-up. The time metric in this model will be the time (months) since study enrollment with predictors including age, gender, time since diagnosis of diabetes and other factors of interest. We will also investigate subgroups of interest using a Forest plot approach. We will plot the means and confidence intervals for the outcome for the two groups using Forest plots to display the total groups and subgroups of interest. We will also generate

longitudinal plots of A1c over time with the means and appropriate exact 95% confidence intervals at each time point. In addition, with the DDS trajectories available, we are able to use machine-learning approaches, such as growth mixture models, to identify clusters of patients with similar trajectories but who are not members of previously defined subgroups. Finally, we will conduct sensitivity analyses to determine if missingness of DDS scores are missing at random or missing not at random. For these analyses, we will use several methods, including the jump-to-reference imputation and the pattern mixture model approaches, to determine if the results using the sensitivity analyses are consistent with the MMRM results, indicating that the missingness is missing at random.

For the secondary outcomes, the change in HbgA1c will be modeled as for the DDS above. The other secondary outcomes can be modeled as binary outcomes and will be modeled as longitudinal logistic models.

Data Management Plan:

All study data will be recorded on a REDCap database established on a secure encrypted server on AWS. All access to the database will be through permissions established by the IT REDCap administrator. Investigators will have to log into the REDCap database to enter or view data. The REDCap database will be developed and implemented by the data management staff of the UMMS Quantitative Methods Core (QMC) with the direction of [name], QMC Director. Logic data checks will be built into the data entry process to help clean the data at entry. Quality control edits will be run to identify inconsistencies and questionable values in the data. The audit trail will be activated for the duration of the study.

Data for analysis will be downloaded directly from REDCap and converted to SAS datasets or R data frames for analysis. The downloaded datasets will be deidentified and are HIPPA as well as 21 CFR Part 11 compliant.

Provider Data:

We will present the data from the provider surveys in a descriptive fashion. For example, we will report the percentage of patients in the CGM arm whose provider found the data useful. We will also do subgroup analyses. Potential subgroups include the type of diabetes, whether or not the diabetes diagnosis is new, and whether or not the participant presented to the ED with hypo- or hyperglycemia.

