Our plan is to conduct a randomized controlled trial of unblinded CGM among people with diabetes who are discharged home after being treated in the ED for diabetes-related emergencies. In conjunction with research assistants, ED clinicians at the University Campus, Memorial Campus, Marlborough Campus, Clinton Campus, and Leominster Campus will identify patients with diabetes (type 1 or 2) and hyper- or hypoglycemia who would benefit from follow up in the UMass Diabetes Center of Excellence (DCOE). The ED physician will place a referral, if necessary, and study staff will help arrange this follow up, scheduling an appointment within 2-3 weeks. In addition to this care coordination, half of the participants will receive a CGM placed by the patient or study staff in the ED, and all patients will receive written instructions about how to handle recurrent hyper- or hypoglycemia.

The primary outcomes will be the rate of attendance at the follow-up visit and be the change in diabetes-related quality of life as measured by the PAID-5 scale and the DDS. We hypothesize that having a CGM will decrease the no-show rate and increase clinic attendance and improved diabetes-related quality of life. Secondary outcomes will include hemoglobin A1c levels over time, ED utilization, emergency medical services utilization, hospitalizations, and major cardiovascular events within 6 months. Finally, we will assess provider satisfaction in the DCOE via a brief survey.

Focusing on a common but rarely studied clinical problem – the ED-to-clinic transition for people with diabetes – this project will promote inter-departmental collaboration between the ED and the DCOE and will directly improve care for people with diabetes, particularly those from disadvantaged groups. In addition to improving care coordination, we will rigorously assess the

usefulness of CGM in a novel context, generating preliminary data for future work and serving as an example for other medical systems regionally and around the world.

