10. STUDY ENDPOINTS*

Our primary outcome The primary outcomes will be the rate of attendance at the follow-up visit and be the change in diabetes-related quality of life as measured by the PAID-5 scale and the DDS.

Secondary outcomes will include A1c levels, recurrent ED or EMS utilization, hospitalizations, and major cardiovascular events. We will also query DCOE providers regarding their satisfaction with the program, including a question about whether the CGM data are helpful for each patient.

Expectation: Our hypothesis is that CGM use after ED discharge will reduce the clinic no-show rate and decrease diabetes-related distress compared to the group with care coordination only.

There are no primary or secondary safety measures being recorded for the purposes of this study.

Safety measures will include number of device questions/concerns expressed by subjects during enrollment through their two-week follow up appointment, reported blood sugar events,

(high/low values), and return visits to clinic/ED/hospitalizations within the 2 week window of enrollment.

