- **Diabetes Center of Excellence Care Coordination:** Study Staff will follow up with ED provider to ensure that patients' have clinically indicated referral to diabetes center of excellence

→ **Appointment scheduling:** RA will make an appointment for the patient before ED discharge, if possible. If this is not possible, RA will contact the patient after discharge to arrange a follow-up appointment.

Outpatient Blood Sugar Monitoring: The CGM will be worn on the participants' upper arm continuously for 14 days (or until it falls off or the patient decides to remove it)

[figure not shown]
Visit #1 (~Day 14-21 Post-Discharge of patient subjects)

- **Documents:**
 - **Visit Data (RA facing)**
 - **Problem Areas in Diabetes (PAID-5) scale/Diabetes Distress Scale and supplemental questions**
 - **Fact sheet for provider subjects**
 - **Provider satisfaction survey**
- **CGM Data:** Biosensor data will be downloaded and reviewed
- **Material Collection:** Study Staff will collect CGM readers
- **Compensation:** Participants will be offered \$10 worth of gift cards to a retail store for completing visit #1.
- **Provider Survey:** immediately following an encounter with a patient subject, the provider taking care of each patient will be contacted by the study team as potential provider subjects. Potential provider subjects subsequently will be sent an email solicitation to participate in a Redcap survey. A fact sheet will be provided with that email. The survey will consist of 4 questions pertaining to their satisfaction with patient subject care coordination and/or their CGM utilization. Providers may be sent multiple surveys if they see multiple subjects who are enrolled in the study. This is the only involvement of the provider subjects.
- **No Shows:** *RAs will reach out to subjects who miss their follow-up appointment to (1) help them reschedule and (2) ask that they fill out the post-intervention questionnaire via an online link (or mailed paper copy or via phone, if desired)*

Follow up Data Collection (~6 months Post-Discharge)

- **Documents:**
 - **6 month follow up datasheet**
- **Data Collection:** The study team will query the EHR to collect follow up data points about enrolled subjects

Figure 1: Procedural Flow Sheet

t

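### The planned analysis of clinic attendance, a primary outcome, never compares the two randomised arms, so as written it cannot test whether CGM reduces no-shows

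*Combined protocol and SAP*

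**What the plan says.** The attendance hypothesis is comparative. Section 4 (Objectives) describes a randomised controlled trial and states: "We hypothesize that having a CGM will decrease the no-show rate and increase clinic attendance". Section 10 (Study Endpoints) names the comparator: "CGM use after ED discharge will reduce the clinic no-show rate and decrease diabetes-related distress compared to the group with care coordination only". Section 11 randomises patients to care coordination alone or with CGM, and Section 25 plans 100 per arm.

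Section 13 (Data Analysis and Management) then sets out attendance as follows.

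- **Sample size.** The aim is given as "we will aim to achieve attendance at 80% of the scheduled clinic visits". The calculation is "For a one-sided test at alpha=0.025 of a single proportion against a standard proportion (0.80), we will have 80% power". The alternative is 0.67, which is 0.13 below the standard, and the result is 83 subjects in the CGM group, raised to about 100 per group for 20% dropout.
- **Unadjusted analysis.** "using an exact test of the frequencies under the presumed population proportion (0.80) and the observed proportion".
- **Adjusted analysis.** A "logistic regression model for the proportion of clinic visits attended as the outcome in the intervention group", with age, gender, time since diagnosis and other factors as predictors.

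The other primary outcome is handled differently: "For the DDS outcome, we will compare the change from baseline to the end of follow-up in the DDS between the two groups".

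**The concern.** Neither attendance analysis uses the control arm. The exact test compares one observed proportion with a fixed 0.80, for which no source is given. The logistic model is restricted to one arm, where treatment is constant; adding it under other factors of interest would not help, because its coefficient is not estimable.

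Meeting or missing 80% in the CGM arm says nothing about CGM itself. Both arms receive appointment scheduling, help after a missed visit and the \$10 payment, and any of these could raise attendance. Only the concurrent randomised controls can separate CGM from the rest of the programme.

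Two further points make the plan harder to apply. The direction of the one-sided test is not stated in words. The outcome is also loosely defined: Sections 4 and 10 speak of attendance at the follow-up visit, while Section 13 speaks of the proportion of scheduled visits attended. Section 11 says "RAs will reach out to subjects who miss their follow-up appointment to (1) help them reschedule" and allows some appointments to be made only after discharge. Nothing says how a rescheduled or never-scheduled visit counts.

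**Working it through.** **1. Is the comparison supplied elsewhere in Section 13?** No. The between-group wording is written for the DDS. The two-group Forest plots sit in the DDS paragraph and show means. The longitudinal logistic models are assigned to the other secondary outcomes, and attendance is primary.

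**2. Reproducing the stated 83.** Inputs from Section 13: null p0 = 0.80, alternative p1 = 0.67, one-sided alpha 0.025, power 80%.

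n = [1.960·√(p0(1−p0)) + 0.842·√(p1(1−p1))]² / (p0−p1)²

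= (0.7840 + 0.3957)² / 0.13² = 82.35, rounded up to 83.

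The arithmetic is right for the test described. The same formula shows which test that is:

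| Null | Alternative | n |
|---|---|---|
| 0.80 | 0.67 | 82.35 → 83 |
| 0.67 | 0.80 | 93.68 → 94 |
| 0.80 | 0.93 | 59.02 → 60 |

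Only the first row gives 83. As sized, the test looks for CGM-arm attendance *below* the 80% aim. The null and alternative may have been swapped by mistake, but the control arm is unused in either direction.

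**3. What the exact test does with 100 CGM patients and null 0.80.** The lower-tail version rejects at 71 or fewer attenders (2.0% chance if the true rate is 0.80). An upper-tail version would need 89 or more (1.3% chance).

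**4. Example.** Suppose 80 of 100 CGM patients attend. The planned lower-tail p is P(X ≤ 80 | n = 100, 0.80) = 0.54, whatever happens in controls.

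- Controls 60/100: difference 0.20; SE = √(0.16/100 + 0.24/100) = 0.0632; 95% CI 0.076 to 0.324; pooled z = 0.20/√(2·0.7·0.3/100) = 3.09, p = 0.002.
- Controls 80/100: difference 0; SE = √(0.32/100) = 0.0566; 95% CI −0.111 to 0.111.

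The planned analysis cannot tell a 20-point benefit from none.

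**5. Power for the comparison the hypothesis needs.** Two-sided 0.05 matches the plan's one-sided 0.025. With p̄ the mean of the two rates pC and pT:

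power = Φ{ [|pT−pC|·√n − 1.960·√(2p̄(1−p̄))] / √(pC(1−pC) + pT(1−pT)) }

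The documents give no expected control rate, so pC is an **assumption**. CGM is held at 0.80. The 80-per-arm column applies if the plan's 20% dropout is excluded from analysis.

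| Assumed control rate | 100 per arm | 80 per arm |
|---|---|---|
| 0.50 | 99.6% | 98.3% |
| 0.60 | 87.6% | 79.4% |
| 0.67 | 54.9% | 46.1% |
| 0.70 | 37.1% | 30.8% |

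Power reaches 80% when the control rate is about 0.621 or lower (100 per arm) or 0.598 or lower (80 per arm).

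For 0.67 against 0.80, p̄ = 0.735 and n per arm = (1.2233 + 0.5196)² / 0.13² = 179.7, or 180. The 0.67 here is borrowed from the CGM-arm calculation; the plan does not offer it as a control rate.

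**The case against.** The strongest reply is that the trial itself can answer the question. Patients are randomised 1:1, the follow-up visit and no-show contact apply to both arms, and the team would presumably compare arms in any case. The first part stands: the defect lies in the written analysis, not in the design or data collection, and that is why it is cheap to mend. The second part does not rescue the plan. An unwritten comparison leaves the test, denominator and rescheduling rule to be chosen later, possibly with the data in view.

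Other points also have some force.

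- Scoring each patient once for the follow-up visit is already what Sections 4 and 10 imply, so it reconciles Section 13 with them and does not invent a new endpoint. The open gap is how rescheduled and never-scheduled visits count, and more than one rule is defensible.
- With no control rate in the documents, low power is not established. At a control rate of 0.50 the planned size is ample.
- The power figures give attendance the full 0.05. The protocol names attendance and distress as primary outcomes without a success rule or alpha split. At an illustrative two-sided 0.025, power at a control rate of 0.60 with 100 per arm falls from about 88% to about 81%.

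These qualify the power statement. None supplies the missing comparison.

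**Conclusion.** The concern holds and must be fixed. Followed as written, Section 13 yields no estimate or test of the effect of CGM on one of the trial's primary outcomes, although the stated hypothesis is explicitly between arms. This conclusion rests on the text alone and needs no assumption.

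The stated 80% power with 83 subjects is correct arithmetic for a different question. Power for the between-arm question depends on the unstated control rate and ranges from above 99% to below 40% over the rates examined with 100 per arm. The direction of the one-sample test should be queried as a possible swap of null and alternative, but that is secondary.

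**What to change.** 1. Make the primary attendance analysis a comparison of the two randomised arms, scoring each randomised patient once as having attended or not attended the post-ED visit at the diabetes center. Say in Section 13 that this replaces the proportion of visits attended.
2. Before analysis, fix one rule for both arms on rescheduled visits, and count patients who are lost, withdrawn or never scheduled as non-attenders. One option for rescheduling is to define attended as keeping the first scheduled appointment and to report attendance after rescheduling separately.
3. Report the between-arm difference with its 95% CI and a two-sided 0.05 test, subject to whatever rule the team states for multiple primary outcomes. Fit the adjusted logistic model to both arms with a treatment term.
4. Report CGM-arm attendance against the 80% aim descriptively. If a test against 0.80 is kept, state its direction and the source of 0.80.
5. Replace the one-sample power sentence with a two-arm statement that labels the control rate as an assumption and shows the range tabulated above, including 0.50.

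**Cost.** Rewording of Section 13 and a small amount of analysis of data already collected in both arms. The stated attendance power becomes less favourable unless the team can justify a control rate of about 0.62 or lower. No extra enrolment is asked for; keeping 80% power for an assumed 0.67 against 0.80 would take about 180 analysed per arm.

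### The attendance test takes 80% as both goal and null, and its stated 80% power is for detecting a shortfall, not the hypothesised increase

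*Combined protocol and SAP*

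**What the plan says.** Section 13 (Sample Size) gives the goal: "For clinic attendance, we will aim to achieve attendance at 80% of the scheduled clinic visits". The next sentence sets the test: "For a one-sided test at alpha=0.025 of a single proportion against a standard proportion (0.80), we will have 80% power to detect a difference". The difference is 0.13, between 0.80 and 0.67, and the sentence ends: "with a sample size of 83 subjects in the CGM group". The enrolment figure follows: "Adjusted for 20% dropout, we will need approximately 100 subjects/group".

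Section 13 (Analysis Strategy) carries the same benchmark into the planned unadjusted analysis, "using an exact test of the frequencies under the presumed population proportion (0.80) and the observed proportion". So 0.80 is the null of the primary attendance test itself and not only a device for sizing the trial.

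Section 4 states the direction of benefit: "We hypothesize that having a CGM will decrease the no-show rate and increase clinic attendance". Section 10 repeats it, with the care-coordination-only group as comparator.

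No section says in words which way the one-sided test points, gives a rule for declaring success on attendance, or says where 0.67 comes from.

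**The concern.** A one-sided test of an improvement normally puts its null at a rate the intervention should beat and its alternative at the rate hoped for. Here the hoped-for rate is the null, and the powered alternative lies below it. Rejecting the null in the powered direction would mean that attendance fell short of 80%, which is the opposite of the finding the investigators expect.

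Two things are at stake. First, the quoted 80% power does not describe the chance of supporting the attendance hypothesis. Second, a result close to the goal will be non-significant, and a report could present attendance not significantly below 80% as success, which this test cannot establish.

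**Working it through.** **Inputs**, all from Section 13 (Sample Size): standard proportion 0.80; other rate 0.67; difference 0.13; one-sided alpha 0.025; power 80%; 83 subjects in the CGM group; 20% dropout; about 100 per group.

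**Step 1: reproduce the 83.** The usual one-sample formula is

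n = [z(0.975)·√(p0(1−p0)) + z(0.80)·√(p1(1−p1))]² / (p1−p0)²

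with z(0.975) = 1.960, z(0.80) = 0.842, √(0.80×0.20) = 0.400 and √(0.67×0.33) = 0.470.

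- Null 0.80, true 0.67: (1.960×0.400 + 0.842×0.470)² / 0.0169 = 82.35, so **83**, as stated.
- Null 0.67, true 0.80: (1.960×0.470 + 0.842×0.400)² / 0.0169 = 93.68, so 94.
- Null 0.80, true 0.93 (the same difference upward): 59.02, so 60.

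None of the other variants tried for null 0.80 and true 0.67 gives 83: continuity-corrected 90, arcsine 90, null variance only 75, alternative variance only 103, two-sided 0.025 99, one-sided 0.05 66. The enrolment figure is 83 × 1.2 = 99.6, about 100.

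The stated size and power therefore belong to a test for attendance below 80%.

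**Step 2: what the planned exact test against 0.80 can show.** Binomial tails, each direction at one-sided 0.025:

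| CGM patients | Significantly below 80% | Neither | Significantly above 80% | Chance of upward rejection if truth is 0.80 |
|---|---|---|---|---|
| 83 | 58 or fewer (69.9%) | 59 to 73 (71% to 88%) | 74 or more (89.2%) | 2.0% |
| 100 | 71 or fewer | 72 to 88 | 89 or more | 1.3% |

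At n = 83 the chance of an upward rejection is 18% if true attendance is 0.85, 68% if 0.90 and 94% if 0.93.

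**Step 3: could non-rejection count as meeting the goal?** At n = 83 the downward exact test has 74.8% power at a true rate of 0.67. An arm truly at 0.67 would thus pass about 100 − 74.8 = 25% of the time, and an observed 59/83 (71%) would pass.

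**Step 4: the roles reversed.** This uses null 0.67 and true 0.80 with the exact upper-tail test. Taking 0.67 as the reference rate is an assumption, because the documents do not call it a historical or control rate.

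| Patients counted | Reject at | Exact power |
|---|---|---|
| 80 (100 less 20% dropout) | 63 or more | 67% |
| 83 | 65 or more | 71% |
| 100 | 77 or more | 81% |

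**The case against.** The best defence is that testing against a performance standard, with power to detect a shortfall, is a recognised design, and that the plan never says the test points upward. This is fair as a description of what the numbers do. It does not remove the mismatch: Sections 4 and 10 hypothesise an increase, and Section 13 gives no other attendance test that addresses it.

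A reader might infer that a CGM arm which meets the goal can never give a positive result. The documents do not support that. An arm truly at 0.80 has a small but non-zero chance of an upward rejection, and an arm well above the goal has a good one (68% at a true 0.90, n = 83). Only an observed rate near 80% is certain to be non-significant.

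A reader might also say that the plan's success criterion is reversed. No success criterion is written. The direction has to be inferred from the order of the two rates and from the formula that returns 83. Nor does the 80% aim name an arm; the CGM group enters with the sample size.

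Finally, if attendance were compared between the randomised arms, the 0.80 benchmark would no longer be needed. That is true. The missing comparison is a separate point, and this one applies for as long as the benchmark test stays.

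**Conclusion.** The concern holds in this form: as powered, the primary attendance test detects a shortfall below 80%, while the stated hypothesis is an increase. The 80% power should not be read as power for that hypothesis. In the upward direction, an arm performing exactly at the goal would reach significance 2.0% of the time with 83 patients or 1.3% with 100, and the observed rate would have to be about 89% or more.

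The inference about direction rests on the 0.80 and 0.67 in Section 13 and on the reproduction of 83. It needs no outside figure. What cannot be concluded is that 0.67 is the usual-care rate, or that reversing the test always keeps 80% power within the planned enrolment. The 81% figure requires all 100 CGM patients to be counted, whereas Section 13 budgets for 20% dropout. Section 11 also lets appointments be arranged after discharge, so some patients might never have a scheduled visit.

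**What to change.** Stop presenting the 80% as power for the attendance hypothesis, and choose one of two courses.

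1. **No new assumption (preferred).** Report CGM-arm attendance with an exact 95% confidence interval beside the 80% goal, drop the power claim for this outcome, and state that a rate not significantly below 80% will not be read as success. This changes wording only.
2. **Keep a benchmark test.** Put the null at a justified lower reference rate, with 0.80 as the design alternative, and state the direction and success rule in words. If 0.67 is to be that rate, give its source and test the null that attendance is at most 0.67. Say who is counted and restate exact power to match: 81% (success at 77 or more of 100) if every randomised CGM patient is included with non-attendance as failure, 71% at 83 evaluable, 67% at 80 evaluable. Counting all 100 needs no extra patients. If 20% are instead treated as lost, the plan's own formula needs 94 evaluable, or 94/0.8 = 117.5, so 118 in the CGM arm.

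Neither course tests the Section 10 hypothesis against care coordination only, which needs its own correction.

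### The 83 for 80% attendance power comes from a normal approximation, not the planned exact test (74.8% at 83, 83.0% at 100), and the detectable DDS difference of 0.40 allows for no loss

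*Combined protocol and SAP*

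**What the plan says.** All of this is in section 13 (Data Analysis and Management) of the combined protocol and SAP, unless noted.

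- **Attendance, sample size.** A one-sided test at 0.025 of a single proportion against 0.80 is said to have 80% power if the true proportion is 0.67, "with a sample size of 83 subjects in the CGM group. Adjusted for 20% dropout, we will need approximately 100 subjects/group". The formula is not named.
- **Attendance, analysis.** The initial unadjusted analysis will be done "using an exact test of the frequencies under the presumed population proportion (0.80) and the observed proportion".
- **DDS, sample size.** The SD comes from a cited study of 267 people with diabetes, where "the standard deviation of the DDS was 1.0 across the three sites in that study". The plan then states: "With 100 subjects in each group, we can detect a difference of about 0.40 in the DDS change between the two groups". For a difference of 0.5, taken from the literature as meaningful, it concludes that "our sample size will achieve power of greater than 80% to detect that difference". No alpha is given for the DDS.
- **DDS, analysis.** The comparison used for sizing is also an analysis: "we will conduct the initial unadjusted analysis as described above in the Sample Size section". Missing scores are expected, since the plan includes "sensitivity analyses to determine if missingness of DDS scores are missing at random or missing not at random".
- **Retrieval of DDS scores.** Under section 11 (No Shows), staff will contact patients who miss the visit and "ask that they fill out the post-intervention questionnaire via an online link (or mailed paper copy or via phone, if desired".
- **Enrolment.** Section 25 rests the 200 patients (100 per arm) on the power analysis in section 13.

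**The concern.** A sample size should be computed for the test that will be run and for the number of patients that test will have. Two statements here do not meet that standard.

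The attendance figure does not belong to the exact test the plan names. A binomial exact test is conservative at this size, so it needs more patients than the approximation for the same power. How far this matters depends on whether dropouts stay in the attendance denominator, and the plan does not say.

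The DDS figure uses the enrolled 100 per group, the number reached after adding the dropout allowance, as if no score would be lost. It also uses the spread of the score at one time as the spread of the change between two times. These are equal only for one particular correlation between baseline and follow-up.

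At stake is whether the justification for 200 patients is correct, and whether a reader can tell what it depends on.

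**Working it through.** **Inputs (section 13).** Null proportion 0.80, alternative 0.67, one-sided alpha 0.025, power 80%, dropout 20%, DDS SD 1.0, 100 per group. *Assumed, because not stated:* two-sided alpha 0.05 for the DDS, and a range of baseline to follow-up correlations r.

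**1. Reproducing 83.** One-sample normal approximation with null and alternative variances:

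n = [(1.960 × √(0.80 × 0.20) + 0.842 × √(0.67 × 0.33)) / 0.13]² = 82.35, rounded up to 83.

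This matches the plan. Approximate power is 79.0% at 80, 80.3% at 83 and 86.4% at 100. Continuity-corrected and arcsine versions both give 90, so the plan used the uncorrected approximation.

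**2. The exact test.** Find the largest c with P(X ≤ c | n, 0.80) ≤ 0.025; power is P(X ≤ c | n, 0.67).

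| n analysed | Reject if attended ≤ | Actual alpha | Exact power |
|---|---|---|---|
| 80 | 56 | 0.0217 | 75.2% |
| 83 | 58 | 0.0185 | 74.8% |
| 85 | 60 | 0.0247 | 79.2% |
| 89 | 63 | 0.0243 | 80.8% |
| 100 | 71 | 0.0200 | 83.0% |
| 104 | 74 | 0.0196 | 84.3% |

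From n = 80 to 88 exact power lies between 69.7% (n = 81) and 79.2% (n = 85). It first reaches 80% at 89, moves above and below 80% after that, and stays at or above it from 99 (79.4% at 98).

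**3. The dropout allowance.** 83 / (1 − 0.20) = 103.75, or 104. The stated figure of about 100 matches 83 × 1.2 = 99.6. Conversely, 100 × 0.80 = 80, not 83. The slip is small: 80 analysed has 79.0% power by the plan's own approximation.

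**4. Reproducing the DDS figure.** The normal formula gives (1.960 + 0.842) × 1.0 × √(2/100) = 0.396; the two-sample t-test gives 0.398. The plan's 0.40 is therefore right for 100 evaluable per group. By the t-test, 80% power for 0.40 needs 99.1 evaluable per group.

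**5. The DDS after loss.** Two-sample t-test, SD of change 1.0:

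| Evaluable per group | Detectable at 80% power | Power for 0.40 | Power for 0.50 |
|---|---|---|---|
| 100 (no loss) | 0.40 | 80% | 94% |
| 90 (10% loss) | 0.42 | 76% | 92% |
| 80 (20% loss) | 0.45 | 71% | 88% |

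**6. The SD of change.** If the score has SD 1.0 at both times, SD of change = √(2(1 − r)). This equals 1.0 only when r = 0.5. At 80 per group:

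| r (assumed) | SD of change | Detectable | Power for 0.50 |
|---|---|---|---|
| 0.3 | 1.18 | 0.53 | 76% |
| 0.5 | 1.00 | 0.45 | 88% |
| 0.7 | 0.77 | 0.35 | 98% |

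The claim of more than 80% power for 0.50 holds if r is at least about 0.37 at 80 per group, 0.29 at 90, or 0.21 at 100.

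**The case against.** The strongest reply is that no decision changes. The target of 200 stands, and so does the plan's actual DDS conclusion, for 0.50 under its own SD. That is correct, and it limits the point to a correction of stated figures.

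For attendance, a patient who disappears after scheduling is naturally a no-show, so all 100 would be analysed and exact power would be 83.0%. That is a reasonable reading, but the plan does not state it and applies a dropout allowance to attendance, which implies the opposite.

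Much of the gap at 83 is discreteness: the attained alpha there is 0.0185, and at 85, where it is 0.0247, power is 79.2%. This is fair as explanation, but a fixed-level exact test has that conservatism, and no n from 80 to 88 reaches 80%. It is also fair that 75.2% at exactly 80 is a local peak (72.8% at 79, 69.7% at 81).

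For the DDS, the 0.40 sentence is conditional on 100 per group and true on those terms, the plan calls its calculation a simplification, and remote completion may keep loss below 20%. At 10% loss, however, power for 0.40 is still 76%. The correlation range is an assumption; no document gives a value. At r = 0.3, power for 0.50 falls below 80% only with the larger loss (80.5% at 90 per group).

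Finally, section 10 states a between-group hypothesis, so a one-sample attendance test may itself need replacing. That is a separate matter, and the DDS restatement is needed either way.

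**Conclusion.** The concern holds. The stated 80% power at 83 is not what the planned exact test delivers: it has 74.8%. With all 100 CGM patients in the denominator exact power is 83.0%; with 80 it is 75.2%. The unstated denominator therefore decides which side of 80% the trial falls on.

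The DDS difference of 0.40 is detectable with 80% power only if essentially every enrolled patient is evaluable. After the stated 20% loss it becomes 0.45, with 71% power for 0.40. Power for 0.50 remains 88%, assuming two-sided alpha 0.05 and r = 0.5.

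Enrolment does not need to rise on these grounds. That statement covers the one-sample attendance test and the DDS comparison as planned. It does not cover a between-arm attendance comparison, for which 0.80 against 0.67 at 100 per group has about 55% power (two-sided 0.05, normal approximation).

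**What to change.** Restate the Sample Size paragraph of section 13.

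- **Attendance.** State the denominator. Say that with 100 CGM patients the exact one-sided 0.025 test against 0.80 has 83.0% power if true attendance is 0.67, and 75.2% if exactly 80 are analysed (about 70% to 75% for 79 to 81). Say that this is one-sample power to detect attendance below 0.80, not power for the comparison with care coordination only. If all 100 are counted, remove the dropout allowance from this sentence.
- **Lost patients.** Count them as not attended only if 0.80 and 0.67 are justified under that definition. To illustrate: if retained patients attend at exactly 0.80 and lost patients count as not attended, the test at n = 100 rejects 0.80 with probability 14.6% at 5% loss, 44.9% at 10% and 94.3% at 20%.
- **DDS.** State the evaluable n, alpha and SD of change. For example: with 80 evaluable per group after 20% loss, two-sided alpha 0.05 and SD of change 1.0 (correlation 0.5), power is 80% for 0.45, 88% for 0.50 and 71% for 0.40; power for 0.50 stays at or above 80% if the correlation is at least about 0.37. If remote completion is expected to hold loss to 10%, use 90 per group: 0.42, 92% and 76%.

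If the attendance test is replaced by a between-group comparison, the attendance figures are superseded and only the DDS restatement remains.

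The cost is text edits to one paragraph, plus a decision on the attendance denominator that the analysis needs anyway. Enrolment and the named tests do not change. The stated DDS figure becomes slightly less favourable.
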